4.4 Study program

Screening and baseline visit (V1)

Potentially eligible patients are screened to determine their eligibility for the study. Complete (Patient Eligibility CRF) and record the number and reason for patients not included.

Prior to enrollment, all patients will be asked to sign an informed consent form to document that they understand the purpose of the study (including procedures, follow-up assessments, and any potential risks involved), have been given the opportunity to ask questions related to this study, and have been informed of treatment alternatives.

At the recruitment visit, the clinician should assess the presence of an oral ulcer, rule out lesions of neoplastic, infectious, or allergic origin, and remove, if present, any causative agents (such as sharp edges of teeth, fillings, crowns, dentures, or braces).

Primary Results:

- Pain intensity. It is measured using the VAS consisting of a 10 cm line [13], where 0 indicates no pain and 10 indicates severe pain.
- Size of each ulcer. A sheet of clear plastic will be applied directly to the ulcer and using a permanent waterproof marker the circumference of the ulcer will be traced and then placed on a graph paper and the number of mm² units included within the drawn area will be counted.

Secondary Results:

- Thermography
- Ulcer Severity Score (USS)

Treatment will be started on the same day with strict infection control measures.

The assessor will open the sequentially sealed envelope corresponding to the patient's recruitment number and write on the CRF the progressive number of the patient contained in the envelope and to which group (A or B) the patient will be assigned.

Patients will receive three anonymous bottles, coded with A, B containing the mouthwash and a scoop. Patients will apply mouthwash. This procedure will be performed under the supervision of the outcome measure which will provide further explanations to patients if necessary.

Participants will be asked to flush with 10mL of mouthwash twice daily ~~directly onto the ulcer~~. Patients were prevented from eating, drinking, or rinsing their mouths for at least one hour after each application.

Observation at 1 week (V2) and at 2 weeks (V3):

- Pain intensity using the VAS scale. The following outcome measures will be recorded by the blinded outcome assessor:
- Size of each ulcer using a clear plastic sheet
- Thermography/ Ulcer severity score (USS)

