7.3 Statistical analysis

Descriptive statistics will be provided in summary tables by group based on the type of outcome measure summarized.

General descriptive statistics for continuous outcome measures will include n (number of observed values), mean with its 95% CI, standard deviation, median, minimum and maximum values. For categorical variables, the number and percentage of subjects with a specific level of the variable will be presented.

This primary efficacy analysis will be performed on ITT, using the null hypothesis of no between-group difference in overall VAS change from baseline between both groups:

$$H_0: \mu_{\text{AfteRapidDNA}} = \mu_{\text{Placebo}}$$

$$H_1: \mu_{\text{AfteRapidDNA}} \neq \mu_{\text{Placebo}}$$

Where μ is the mean change from baseline on Day 7 within the given product.

This hypothesis will be tested with an Analysis of Variance (ANOVA) with baseline values of VAS as a covariate. The groups will be compared to the bilateral significance level of 5%.

The assumption of normality will be verified by means of QQ graphs and by plotting the studentized residuals with respect to the expected values of the variable. If there are strong indications of non-normality of the data, the Wilcoxon Rank-Sum Test will be used to test the hypothesis of no median difference between buccacollutorio and placebo at Day 7 in a nonparametric manner. Summaries for each treatment group will include sample size, mean, median, standard deviation, minimum, maximum, Wilcoxon Rank-Sum test p-value, Hodges-Lehman point estimates of median treatment difference, and its 95% confidence interval.

From the Day 7 endpoint ANOVA model, a least squares estimate (LSMEANS) of the group effect and group difference (both with 95% confidence intervals) will be displayed along with the p-value of the difference between the groups.

Analysis will also be performed for the PP Analysis Set to test the robustness of the results.

For secondary quantitative efficacy variables, cross-treatment group comparison of change from baseline will be done by the same ANOVA model used in the primary efficacy analysis. Categorical derived variables (complications/adverse events) will be compared via a chi-square test or Fisher's exact test, as appropriate (chi-square test will be used if all groups have sufficient observations,

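### If the residual plots look non-normal, the primary VAS analysis drops its baseline adjustment for a loosely defined Wilcoxon test; one fixed ANCOVA with a rank-ANCOVA beside it would be better.

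*Combined protocol and SAP*

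**What the plan says.** All of this stands in section 7.3 of the combined protocol and SAP, except where noted.

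- Primary quantity: "Where μ is the mean change from baseline on Day 7 within the given product".
- Primary test: "This hypothesis will be tested with an Analysis of Variance (ANOVA) with baseline values of VAS as a covariate", two-sided at 5%, in the ITT population. This is an ANCOVA.
- Assumption check: "The assumption of normality will be verified by means of QQ graphs and by plotting the studentized residuals" against expected values. No numerical criterion is given.
- Fallback: "If there are strong indications of non-normality of the data, the Wilcoxon Rank-Sum Test will be used". No covariate or stratification is mentioned for it. Its hypothesis is one of equal medians in the two groups at Day 7. It is reported with a p-value and a Hodges-Lehmann estimate with its 95% interval.
- A following paragraph has the ANOVA least-squares means, their difference and its p-value displayed, without making this depend on the normality check.
- The VAS is a 10 cm line, "where 0 indicates no pain and 10 indicates severe pain" (section 4.4).
- The statistician stays blinded until the analysis is performed, and the A/B codes are broken when the manuscript is written (section 3, Study Design).

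**The concern.** The planned model uses baseline VAS to sharpen the comparison in a trial of 60 patients. The fallback drops that information, although a rank-based test that keeps it needs only the same data. Three things are also left open: what counts as a strong indication, which variable is ranked, and how a median difference relates to the mean difference in the primary hypothesis. The choice of test can matter. In simulations without a floor, with a true difference of 0.82 and 29 per arm, ANCOVA and the Wilcoxon test on change disagreed about significance in 16-39% of trials.

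A scale bounded at 0, in a condition that can heal within a week, could well give residuals that look non-normal. How often is unknown, because the documents give no expected VAS means.

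**Working it through.** **The plan's own figures.** Section 7.1 gives difference 0.820, SD 1.80, 80% power and 29 per group. Check: n = 2 × (1.96 + 0.842)² × (1.80/0.820)² ≈ 2 × 7.85 × 4.82 ≈ 76 per group. So 29 does not reproduce, and 29 per group gives about 40% power. At SD 1.80, 29 per group fits a difference of about 1.35. That is a separate problem, but it explains why both 0.82 and 1.35 are used below.

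**Step 1: what dropping baseline costs, no floor, normal errors.** Let σ be the SD of the VAS score at each visit and ρ the baseline-to-Day 7 correlation (not in the documents; 0.3/0.5/0.7 assumed). The variance of the group difference in means is proportional to:

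- ANCOVA: σ²(1 − ρ²)
- change score: 2σ²(1 − ρ)
- Day 7 score: σ²

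Information lost against ANCOVA is therefore 1 − (1 + ρ)/2 = (1 − ρ)/2 = 35/25/15% for change, and ρ² = 9/25/49% for the Day 7 score. Which reading is worse depends on ρ, so the missing statement of what is ranked matters.

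**Step 2: power when the fallback is used, with a floor.** Simulation: 30 per arm, VAS clipped to 0-10, baseline mean 5, SD 1.8, control Day 7 mean 2.0. The means, the correlation and the use of 1.8 as the SD of the score are assumptions.

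| Power, ρ = 0.3/0.5/0.7 | Difference 1.35 | Difference 0.82 |
|---|---|---|
| Wilcoxon on change | 49/62/79% | 24/30/44% |
| Wilcoxon on Day 7 score | about 78% | 37-39% |
| Rank-ANCOVA | 81/86/95% | 41/46/61% |

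At 1.35 the gap to rank-ANCOVA is 81 − 49 = 32, 86 − 62 = 24 and 95 − 79 = 16 points if change is ranked, and about 3, 8 and 17 points if Day 7 scores are. Adding a control mean of 3.5, the gaps across all scenarios are about 5-32 and 2-24 points. Ordinary ANCOVA was close to rank-ANCOVA at control mean 2.0 and difference 1.35 (about 80/87/95%).

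**Step 3: power of the plan as a whole.** The switch happens only if the plots trigger it. A Shapiro test on the residuals at 5% served as a stand-in. At difference 1.35 it fired in 16-58% of trials with control mean 2.0, and in 6-9% with 3.5. At mean 2.0 the switched procedure had about 62/78/92% power ranking change and 79/84/92% ranking Day 7 scores. Over all scenarios the loss was about 0-17 points ranking change and 0-3 ranking Day 7 scores. One-point differences between runs are simulation error.

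**Step 4: skewed or heavy-tailed errors, no floor.** Here there are 29 per arm, the difference is 0.82 and the SD of change is 1.80.

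| Errors, ρ | ANCOVA | Wilcoxon, change | Wilcoxon, Day 7 | Rank-ANCOVA |
|---|---|---|---|---|
| Normal, 0.5 | 50% | 38% | 37% | 47% |
| t with 3 df, 0.5 | 57% | 50% | 50% | 67% |
| Lognormal, 0.5 | 62% | 63% | 63% | 87% |
| Lognormal, 0.7 | 58% | 74% | 32% | 73% |

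**Step 5: type I error.** Each test on its own held about 4-5%. Switching on the stand-in trigger gave about 5-6%.

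**The case against.** The strongest reply is that this is a wording matter. The fallback exists for skewed data, and there the unadjusted Wilcoxon can beat ANCOVA (74% against 58%, lognormal, ρ = 0.7). That stands, so it would be wrong to say that the fallback always discards power. It does not rescue this choice of fallback: a rank test that keeps baseline is usually better still and at worst about equal (73% against 74%), and the Wilcoxon's advantage in that case disappears if Day 7 scores are ranked (32%).

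It also stands that the step 2 figures describe the fallback once used, not the trial, and that they rest on VAS means, correlations and a 1.35 difference that the documents do not give.

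Two stronger readings are tempting, and the documents support neither.

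- *That the plan leaves two competing primary p-values.* The text substitutes the Wilcoxon test for the ANOVA once the trigger is met. The later paragraph on displaying ANOVA results is not made conditional, which is untidy, but it does not create a second primary test.
- *That the switch inflates type I error to 6-9%.* That range arises only if the smaller of the ANCOVA and Wilcoxon p-values is taken, which the plan does not allow. Blinding under the A/B codes also limits a choice driven by direction, though it could not prevent a choice made after both p-values were seen.

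**Conclusion.** The point holds in limited form. The fallback removes the baseline adjustment, has no stated criterion, does not define its variable and changes the hypothesis from a mean to a median difference. When used on a floored VAS it loses about 5-32 points of power to rank-ANCOVA if change is ranked, and about 2-24 if Day 7 scores are. For the plan as a whole the loss is about 0-17 or 0-3 points, with a Shapiro test standing in for the plots. All these sizes depend on the assumed means, correlation and error shape. The false-positive rate is not the problem. This is a cheap improvement worth making, not a flaw that invalidates the analysis.

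**What to change.** In section 7.3:

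1. Name ANCOVA of Day 7 VAS change on group and baseline VAS as the single decisive primary test, and delete the plot-based switch. The plots can stay as diagnostics.
2. Replace the Wilcoxon fallback with a pre-specified rank-ANCOVA: rank Day 7 VAS and baseline VAS over all patients, then regress the Day 7 ranks on the baseline ranks and group. Report it always, as a sensitivity analysis.
3. Keep the Hodges-Lehmann estimate as descriptive, and state whether it uses the Day 7 score or the change.

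The cost is a few sentences and a few lines of SAS, with no effect on patients, visits or data collection. There are two small downsides. Rank-ANCOVA gives no estimate in VAS points, so the least-squares mean difference and its confidence interval must stay beside it. With strongly skewed errors, fixing ANCOVA can also cost power against a rank test, and the sensitivity analysis would show this without changing the decisive result.

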6.1 Evaluation of the primary objectives

- Pain intensity. It will be measured using the VAS consisting of a 10 cm line [13], where 0 indicates no pain and 10 indicates severe pain.
- Size of each ulcer. A sheet of transparent plastic will be applied directly to the ulcer and using a permanent waterproof marker the circumference of the ulcer has been traced and then placed on a graph paper counting them units of mm² included within the drawn area. Treatment will begin on the same day with strict infection control measures.

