6.2 Evaluation of secondary objectives

- a. Thermography [16,17,19]
- b. Ulcer severity Score (USS) [18]:

Ulcer severity Score (USS)

	Characteristics of the lesion	Score	Description of the USS
Average number of injuries			Score = average number of ulcers in a culture Maximum score = 20
Average lesion size (in mm)			Score = mean size of ulcers in mm Maximum score = 20
Average duration of lesions (in weeks)			Score = number of 1/2 weeks i.e. Half a week (3 days) scores 1, one and

			a half weeks (10 days) scores 3. Maximum score = 10
Injury-free period (in weeks)			Score = 10 minus the average ulcer-free period in weeks Maximum score = 10 (never ulcer-free)
Patient-perceived pain (scaled from 0–10)			1 for slight discomfort in the presence of ulcers. ¹⁰ for excruciating ulcers that interfere with eating and speaking Maximum score = 10
Site of injury	Group 1 Labial mucosa Buccal mucosa Buccal sulcus Soft palate Belly of the tongue Floor of the mouth Group 2 Hard palate Adherent gum Alveolar ridge Dore of tongue Tonsils Tonsil pillars Uvula Oropharynx		Score = total of sites involved 1 for each site of group 1 (non-keratinized mucosa) 2 for each site of group 2 (keratinized, specialized) Maximum score = 10
Scarring	Yes/No		USS Total

Complications and adverse events: Any post-operative complications and adverse events (mucosal irritation, allergic reactions, etc.) will be recorded and reported by study group by blinded evaluators in the Complications, protocol deviation, and drop out.

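### Section 7.3 names baseline VAS as the only covariate, so thermography and USS are not clearly adjusted for their own baselines and ulcer area has no clearly assigned model

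*Combined protocol and SAP*

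**What the plan says.** Section 7.3 gives one hypothesis and one model. The hypothesis concerns VAS, and the parameter "is the mean change from baseline on Day 7 within the given product". The model is stated as follows: "This hypothesis will be tested with an Analysis of Variance (ANOVA) with baseline values of VAS as a covariate".

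The other outcomes are covered by one sentence. Its scope is the secondary quantitative outcomes, with the two arms compared on how far each has moved since baseline, and it says that this "will be done by the same ANOVA model used in the primary efficacy analysis". It names no covariate. Nothing in 7.3 says that the covariate changes with the outcome, or that baseline VAS is kept on purpose.

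Thermography and USS are secondary in sections 4.4 and 6.2. Ulcer size is listed beside VAS among the primary results in 4.4 and again in 6.1 ("Size of each ulcer. A sheet of transparent plastic will be applied directly to the ulcer"). It also appears in the null hypothesis of section 2. Section 7.3 does not mention it.

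The study flowchart schedules VAS, ulcer measurement, thermography and USS at V1, so every outcome has its own baseline value.

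**The concern.** For VAS, the covariate in 7.3 is the outcome's own baseline, which is the standard and efficient choice. Carried over unchanged to another outcome, it becomes a different variable that may be only weakly related to that outcome's change. The change score then keeps most of the between-patient spread in starting values, and a chance difference between arms at baseline is not corrected.

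This matters most for ulcer area. Area is a count of squares on graph paper ("the number of mm² units included within the drawn area will be counted"), and a reduction in mm² cannot exceed the area at the start. Change is therefore tied to baseline area, and a few large ulcers can dominate an analysis that ignores it.

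There is also a problem of specification. With about 30 patients per arm, two analysts could fit different covariates to the same outcome, both claim to follow 7.3, and reach different conclusions.

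**Working it through.** **Figures in the plan.** The plan gives no SD, correlation or effect size for ulcer area, thermography or USS, so no stated figure on this point can be reproduced. Section 7.1 names no outcome. Its inputs (difference 0.820, SD 1.80, two-sided 5%, 80% power) give n = 2 × (1.960 + 0.842)² × 1.80² / 0.820² ≈ 76 per group, not 29. That is a separate matter. Here it means only that the 80% used in step 2 is a benchmark and not the trial's actual power.

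**Step 1: general case, equal SDs.** Let ρ be the correlation between an outcome's baseline and follow-up values (assumed), with SD 1 at both times.
- Residual variance of change without own-baseline adjustment: 2(1 − ρ).
- Residual variance with own baseline as covariate: 1 − ρ².
- Ratio: 2/(1 + ρ). Information lost: 1 − (1 + ρ)/2 = (1 − ρ)/2.
- ρ = 0.3, 0.5, 0.7 gives losses of 35%, 25%, 15%.

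This treats baseline VAS as unrelated to the outcome. Any correlation reduces the loss.

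**Step 2: baseline VAS as covariate, SDs allowed to differ.** Let k = follow-up SD / baseline SD, and q = correlation of the outcome's baseline with baseline VAS. Assume VAS relates to follow-up only through the outcome's baseline. All three inputs (k, ρ, q) are assumptions.
- Own-baseline covariate: k²(1 − ρ²).
- Baseline-VAS covariate: 1 + k² − 2ρk − q²(1 − ρk)².
- Power with baseline VAS, when own-baseline adjustment has 80%: Φ(2.802/√ratio − 1.960).

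Worked cases at ρ = 0.5, q = 0.3:
- k = 1: 0.9775/0.75 = 1.30, power 69%.
- k = 0.5: 0.6994/0.1875 = 3.73, power 30.5%.

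Over ρ from 0 to 0.9 and q from 0 to 0.5:

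| k | Power with baseline VAS (own baseline = 80%) |
|---|---|
| 1 | 51–79% |
| 0.75 | 39–60% |
| 0.5 | 18–34% |
| 0.25 | 6–12% |

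With equal SDs the variance ratio cannot exceed 2, so the loss is at most about 29 points. Power falls below half of the reference mainly when follow-up SD is about half the baseline SD or less. Simulation with 29 per arm agreed: about 65% (k = 1) and 30% (k = 0.5) at ρ = 0.5, q = 0.3, against 78% for own baseline. Type I error with the VAS covariate was 4.5–5.1%.

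**Step 3: illustration for ulcer area.** Assumed inputs, none from the documents: 30 per arm, median area 20 mm², log-SD 0.4–0.7, mean remaining fraction 45% (placebo) and 25% (test) with SD 0.20, VAS–area correlation 0.2–0.5.

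| Analysis | SE (mm²) | Power |
|---|---|---|
| Change, baseline VAS covariate | 1.8–3.7 | about 27–64% |
| Change, baseline area covariate | 1.2–1.6 | 85–94% |
| Rank ANCOVA, ranked baseline area | – | 92–95% |
| Wilcoxon on change | – | about 34–62% |
| Wilcoxon on Day 7 values | – | about 71–86% |

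At log-SD 0.4, power goes from about 94% with baseline area to 58–64% with baseline VAS. At log-SD 0.7 it goes from about 86% to 27–31%.

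**The case against.** **Baseline VAS may not be intended for the other outcomes.** It is named in a sentence about VAS, where it is the outcome's own baseline. A statistician could fairly take the later sentence to mean the same form of model with the matching baseline. This stands: the documents do not establish that the sponsor means to adjust thermography or USS for pain. But on that reading the covariate is still unwritten for every outcome except VAS, and the same clarification is needed.

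**Ulcer area may not fall under the sentence.** The sentence is limited to secondary variables, and ulcer area is listed as primary. This also stands. A reader might infer that 7.3 adjusts ulcer area for baseline VAS; the text supports only that ulcer area is either covered by that sentence or left without an analysis.

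**Non-normality may displace the model.** Section 7.3 moves to a Wilcoxon rank-sum test on strong non-normality, which is likely for skewed areas with zeros at healing. The 27–64% is therefore not reliably the power of the analysis that would be run, and a rank test is not dominated by a few large ulcers. This stands in part. The text does not settle whether the fallback extends beyond VAS, or whether it would use change or Day 7 values. It is also unadjusted, so naming a covariate in the parametric model alone would not secure the gain.

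**Baseline VAS is not irrelevant to USS.** USS contains pain and lesion-size items (section 6.2), so the covariate may do some work there. This stands; the loss for USS cannot be quantified from the documents.

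**Conclusion.** The point holds as a gap in specification with a cost in precision. Followed as written, 7.3 adjusts thermography and USS for baseline VAS; read generously, it leaves their covariate unstated. Ulcer area has no clearly assigned analysis on either reading.

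The size depends on inputs that the documents do not give. With equal SDs, the information lost is 35%, 25% or 15% at correlation 0.3, 0.5 or 0.7. For ulcer area the loss may be larger, because areas that heal toward zero also lose spread; the simulated 27–64% against 85–94% illustrates this on assumed inputs and does not estimate this trial's power.

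Two stronger inferences are not supported. One is that most of the power for ulcer area is lost: in the simulation that happens only with strongly skewed areas, and at log-SD 0.4 the loss is about 30–36 points from 94%. The other is that the comparison is invalid or biased: randomisation protects the test, and type I error stays near 5%. What is at stake is precision and the handling of chance baseline imbalance.

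**What to change.** Replace the sentence on secondary quantitative variables in 7.3 with wording to this effect:

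> Ulcer area, thermography and USS will each be analysed by ANCOVA of change from baseline, with group and the baseline value of that same outcome as covariate. For ulcer area, if the normality assumption fails, a rank ANCOVA (ranked follow-up area on group and ranked baseline area) will replace the unadjusted Wilcoxon rank-sum test.

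Then reconcile the status of ulcer area: sections 4.4 and 6.1 list it as primary, while 7.3 gives a primary hypothesis and model for VAS only.

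The cost is a few lines of text settled before unblinding. All baseline values are already collected at V1, and no extra patients, visits or measurements are needed.

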7 ANALYSIS

7.1 Sample size

A sample size of 29 subjects for each group (power 80%) to detect a significant difference in means of 0.820 assuming the common standard deviation is 1.80 using a two-group t Student test with a significance level for $p<0.05$. Considering a 3% drop out, a sample of 30 subjects per study group will be enrolled.

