otherwise Fisher's exact test will be used). All statistical comparisons will be conducted at the significance level 0.05. SAS version 9.4 will be used for scanning.

8 Data management

An electronic CRF (eCRF) will be completed by the Investigator and/or his/her delegate.

All patients who sign the informed consent will be archived. A minimum set of information is required for patients who are screened but not randomized: date of signed informed consent, demographics, assessment of inclusion/exclusion criteria where applicable, primary reason for non-continuation, adverse events, and any concomitant medications.

Front-end change checks will be performed at the time of data collection, and back-end change checks will be used by the Data Manager to check for discrepancies and ensure data consistency and completeness.

Administrative practices and data management

Medical record forms (CRFs) must be completed at the time of data collection. The complete CRF memory device containing the digitized clinical images should be attached to each patient's study file.

All data required for this study will be collected using paper-based CRFs. CRFs will be kept in a secure, locked location that will only be accessed by the Principal Investigator and the data collector. The data will also be accessible to the sponsor for monitoring and evaluation purposes at its discretion. After completion of the 1-week follow-up, copies of all CRFs will be sent to the investigator who will check the data and store them in a protected computer with a password known only to him. The data will be processed by an expert statistician. The patient's identity will be protected and known only to the study participants listed in this protocol.

Case Report Forms (CRFs)

- Patient informed consent form
- CRF Patient Eligibility
- CRF Rating
- Complications, protocol deviation and CRF drop-out

Changes and violations of the Protocol

Changes to this protocol may be necessary, and protocol violations are likely to occur. Any protocol violation should be reported in the "Complications, Protocol Deviation, and CRF Dropout" section. If you experience any problems, contact your studio monitor immediately.

Data Ownership

The data belongs to the sponsor.

Essential bibliography

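### Complications are compared between arms only by a chi-square or Fisher test at 0.05, with no risk difference or confidence interval, at about 30 patients per arm

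*Combined protocol and SAP*

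**What the plan says.** All of this is in the combined protocol and SAP.

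- **Test (7.3 Statistical analysis).** "Categorical derived variables (complications/adverse events) will be compared via a chi-square test" or by Fisher's exact test. The choice between them is worded as "chi-square test will be used if all groups have sufficient observations", and "otherwise Fisher's exact test will be used". No threshold for sufficiency is given.
- **Level (7.3).** "All statistical comparisons will be conducted at the significance level 0.05". Safety is not exempted.
- **Description (7.3).** For categorical variables, "the number and percentage of subjects with a specific level of the variable will be presented". Section 6.2 adds that complications and adverse events, with mucosal irritation and allergic reactions as examples, are reported by study group.
- **Estimates for the other comparisons (7.3).** The primary comparison gets a least squares group difference with a 95% CI. Its nonparametric fallback gets a Hodges-Lehmann difference with a 95% CI. Secondary quantitative variables use the same model as the primary.
- **Size (7.1 Sample size).** "a sample of 30 subjects per study group will be enrolled". The calculation concerns a difference in means. No complication rate and no power for safety are stated.
- **Allocation (3 Study design).** Simple randomization, which does not fix the split at 30:30.

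**The concern.** Safety is the one between-group comparison in 7.3 that is planned as a p-value alone. In a trial sized on a continuous efficacy outcome, a test on a few events will usually be non-significant whether or not the test mouthwash irritates the mucosa. Such a p-value does not tell the reader how large an excess remains compatible with the data. Near the boundary, the result can also turn on which of the two named tests is run, or on one patient more or less in a denominator. What is at stake is how the complication table can be interpreted. The efficacy analysis is not affected.

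**Working it through.** **Inputs.** From the documents: 30 per arm (7.1), level 0.05, chi-square or Fisher (7.3). Assumed: two-sided testing, which 7.3 states for the primary comparison only, and every event count and rate below, because the documents give none. There is no safety figure in the plan to reproduce.

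**1. The same table under the named tests: 5/30 against 0/30.**

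- *Fisher.* The probability that all 5 events fall in one given arm is C(30,5)/C(60,5) = 142,506/5,461,512 = 0.0261. With equal arms the opposite table is equally likely, so the two-sided p = 2 × 0.0261 = 0.052.
- *Uncorrected chi-square.* N(ad − bc)²/(product of margins) = 60 × (5 × 30 − 25 × 0)²/(5 × 55 × 30 × 30) = 1,350,000/247,500 = 5.45, so p = 0.0195.
- *Yates-corrected chi-square.* 60 × (150 − 30)²/247,500 = 3.49, so p = 0.062.

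The expected number of events is 5/2 = 2.5 per arm. The common convention of expected counts of at least 5 would select Fisher, but the plan does not state that convention.

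**2. One patient fewer in the arm with events: 5/29 against 0/30.**

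C(29,5)/C(59,5) = 118,755/5,006,386 = 0.0237. The opposite table has probability C(30,5)/C(59,5) = 142,506/5,006,386 = 0.0285. That is larger, so it is not added, and Fisher's two-sided p = 0.024. Against step 1, the p-value more than halves for one patient in the denominator.

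**3. Other tables at 30 against 30 (Fisher).** 6 against 0 gives p = 0.024, so six events against none is the smallest count that reaches 0.05. 7 against 1 gives p = 0.052.

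**4. Power.** Summing the binomial probabilities of all tables at 30 against 30 with two-sided Fisher p < 0.05:

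| Assumed true rates | Power |
|---|---|
| 15% against 2% | 18% |
| 16.7% against 0% | 38% |
| 20% against 2% | 41% |

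**5. What an interval adds.** The Newcombe interval combines the Wilson limits (l, u) of each arm: lower = d − √[(p₁ − l₁)² + (u₂ − p₂)²], upper = d + √[(u₁ − p₁)² + (p₂ − l₂)²].

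For 5/30 against 0/30, the Wilson limits are 0.0734 to 0.3356 and 0 to 0.1135, and d = 0.1667:

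- lower = 0.1667 − √(0.0933² + 0.1135²) = 0.0197
- upper = 0.1667 + √(0.1690² + 0²) = 0.3356

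| Events | Difference (points) | Newcombe 95% CI | Fisher p |
|---|---|---|---|
| 5/30 vs 0/30 | 16.7 | 2.0 to 33.6 | 0.052 |
| 5/29 vs 0/30 | 17.2 | 2.3 to 34.5 | 0.024 |
| 7/30 vs 1/30 | 20.0 | 2.4 to 37.8 | 0.052 |
| 3/30 vs 1/30 | 6.7 | −8.2 to 22.5 | 0.61 |

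The first two rows have almost the same interval although their p-values lie on opposite sides of 0.05. In the last row, p = 0.61 gives no hint that an excess of about 20 points remains compatible with the data. Even with no events in an arm of 30, the exact 95% upper limit for that arm's rate is 1 − 0.025^(1/30) = 11.6%.

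The Newcombe interval is not derived from Fisher's test, so the two can disagree, as in rows one and three. The interval method should therefore be named in advance.

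**The case against.** The strongest case on the other side has four parts.

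- **The raw data will be shown.** Counts and percentages by group are required, so 5 (16.7%) against 0 (0%) would be visible, and a reader could compute an interval from them. This stands. It rules out saying that complications are judged by a significance test alone, and it keeps the point minor. Counts still do not state what excess the data exclude.
- **No conclusion of equal tolerability is planned.** A reader might infer that 5 of 30 against none would be reported as no difference. The documents do not support that: they contain no tolerability hypothesis, no safety decision rule and no wording for a non-significant result.
- **The example lies at the edge.** Six against none is significant by Fisher, five against none is significant by uncorrected chi-square, and an exact 30:30 split is not assured. A flat statement that such an excess would be missed is therefore not established, nor is it true that the test cannot flag visible reaction rates. What stands is that the outcome is unstable near the boundary, partly because the rule for choosing the test has no threshold.
- **Low power for adverse events is normal in a small efficacy trial, and a chi-square or Fisher test is conventional.** This is true, and no larger sample is asked for. Low power is itself the reason to show an interval.

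**Conclusion.** The point holds as a cheap improvement, not as a flaw that threatens the trial. The only planned between-group inference on complications is a test at 0.05 without an estimate or interval, while the other comparisons in 7.3 have one. Its power at 30 per arm is 18% to 41% for the assumed excesses of 13 (15 − 2) to 18 (20 − 2) points. For 5 events against none, p ranges from 0.0195 to 0.062 across test variants at 30:30, and Fisher's p moves from 0.052 to 0.024 with one patient fewer in the arm with events. These sizes rest on hypothetical rates and counts, two-sided testing and arms of about 30. The absence of an interval rests on the text alone.

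It would go too far to require that a tolerability conclusion be drawn from the upper confidence limit. The plan sets no tolerability margin against which to judge it.

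**What to change.** In 7.3, replace the sentence on categorical derived variables with wording to this effect: for each arm, the number and percentage of patients with at least one complication or adverse event will be given, with the risk difference (test minus placebo) and its 95% CI by one named method (Newcombe or exact). Safety will be interpreted from the estimate and interval, not from whether p is below 0.05. Any p-value that is kept is descriptive, and the criterion for chi-square or Fisher is then stated.

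The cost is one sentence and one table column, with no change to data collection, sample size or conduct. The safety statement becomes slightly less favourable, because the interval will show that a sizeable excess often cannot be excluded.
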